Appendix A

Data Collection Schedule

	Study entry	Beginning of treatment period	After 2 week treatment period	6 months of age	6-12 months of age	Discharge through 12mo of age
Consent and medical history	Х	•				
Breathing test*		X	X	Х		
Blood sample**			Х			
Monthly breathing questionnaire by phone						Х
Neurodevelopmental testing					Х	

^{*}A syrup to make child sleepy will be given only at the 6 month breathing test
** Collected when a sample for clinical care is being done

Extending CPAP Therapy in Stable Preterm Infants to Increase Lung Growth and Function: A Randomized Controlled Trial

The eCPAP STUDY

Statistical Analysis Plan (SAP) Version 1: August 20, 2023

Version Date	Version	
August 20, 2023	1	Initial release

Specific Aims:

We hypothesize that extended CPAP (eCPAP) in stable preterm infants in the neonatal intensive care unit (NICU) will increase alveolar volume (V_A), lung diffusion capacity (DLCO), and forced expiratory flows (FEFs) measured at approximately 6 months corrected age compared to stable preterm infants who had CPAP discontinued by clinical criteria. Infants stratified by gestational age will be allocated to CPAP discontinuation (dCPAP, usual care) or eCPAP for 2-weeks to address the following Specific Aims:

Specific Aim 1 / Primary Outcome:

Establish that 2 additional weeks of CPAP in the NICU for stable preterm infants increases alveolar volume at approximately 6 months of corrected age compared to infants who have CPAP discontinued, usual care.

Specific Aim 2 / Secondary Outcomes:

Establish that 2 extra weeks of CPAP in stable preterm infants increases DLCO and FEFs at approximately 6 months of corrected age versus infants who have CPAP discontinued, usual care.

Specific Aim 3 / Exploratory Outcomes:

Evaluate whether 2 extra weeks of CPAP in stable preterm infants results in lower respiratory morbidity and/or improved neurodevelopmental outcomes through 12 months of corrected age compared to infants who had CPAP discontinued, usual care. This will provide pilot data for a future multi-center randomized trial.

Population:

Screened:	All infants delivered at OHSU at ≤ 32 and 6/7 weeks gestation and who required CPAP
-----------	---

for \geq 24 hours.

Screen Failed: Met any exclusion criteria.

Enrolled: All infants consented into study.

Intention-to-treat

(ITT): All enrolled infants who met eCPAP stability criteria prior to 35 weeks of postmenstrual

age/ corrected gestational age and were randomized or assigned to a treatment group

will be analyzed in that group.

Per protocol: Only randomized or assigned infants¹ who received the treatment intervention as

allocated will be included, that is who received the allocated treatment intervention for ≥

9 days of the 14 day treatment period

As treated: All randomized or assigned infants will be analyzed based on the treatment actually

received regardless of the allocation assignment.

Completed: All randomized or assigned infants who had not discontinued and had not been

withdrawn.

85 Discontinued: All randomized or assigned infants who were withdrawn by investigator.

87 Alveolar volume

completed: Have a completed procedure with a corrected age of approximately 6 months (allowable

range of 4 - 12 months corrected age).

DLCO completed: Have a completed procedure with a corrected age of approximately 6 months (allowable range of 4 - 12 months corrected age). FEFs completed: Have a completed procedure with a corrected age of approximately 6 months (allowable range of 4 - 14 months corrected age). Clinical Respiratory Outcome Done: Have at least one respiratory questionnaire completed at 4 months of corrected age or

Neurodevelopmental

 Outcome Done: Have a neurodevelopmental exam completed at less than or equal to 16 months of

corrected age.

¹ 2nd twin is assigned to same arm as 1st twin that is randomized

Data Analyses:

- 1) Outcomes data will initially be analyzed by ITT, according to the treatment arm the infants were randomized or assigned to, regardless of treatment adherence. **THIS IS THE PRIMARY ANALYSIS**.
- 2) Outcomes data will secondarily be analyzed by per protocol analyses, that is only the infants who received the intervention as randomized or assigned will be included.
- 3) Outcomes data will be analyzed by "as treated analyses" by the treatment received.

POWER AND STATISTICAL CONSIDERATIONS/ANALYSIS

Statistical Analysis. All outcomes will be analyzed by a statistician blinded to the infants' treatment assignments by intention to treat. Maternal and infant characteristics will be compared using the independent-samples t-test for continuous measures (or the Wilcoxon–Mann–Whitney test for nonnormal distributions) and the chi-square test for categorical variables. We will examine the distributions of continuous variables and use alternative approaches such as transformation or nonparametric methods in cases of violation to the normal distribution assumption. We will examine the frequency distribution of all categorical variables and adopt exact inference procedures in cases of zero or small cell size. All analyses will be conducted using the SAS 9.4 (SAS Institute, Carey, NC).

Specific Aim 1 (Primary Outcome): General linear mixed models (GLMMs) models will be used to compare the primary outcome of alveolar volume (V_A) between the eCPAP and CPAP discontinuation group while adjusting for gestational age at delivery (randomization stratification variable) and other baseline variables that are found to be statistically different between the two groups. Since the lung function measures are highly dependent on infant length and sex, we will further adjust for length and sex in the GLMMs as indicated. In order to adjust for intra-twin correlations, generalized estimating equations (GEEs) with the linear link function will be used to model V_A . The GLMMs can be performed using the GEE estimation approach. Intention to treat analysis will be used for the primary analysis of all aims.

Specific Aim 2 (Secondary Outcomes): Lung diffusion capacity (DLCO) and forced expiratory flows (FEFs) and specifically FEF $_{50}$ will be analyzed with the same general approaches described for the primary outcome of V_A in Specific Aim 1.

FRC measurements in the NICU done pre and post randomization and FEF₂₅₋₇₅, FEF₇₅ done at 6 months of corrected age will be analyzed with the same general approaches as above in Specific Aim 1.

Specific Aim 3 (Exploratory Outcomes): Logistic regression models will be used to compare the incidence of wheeze and the incidence of wheeze and cough between the two groups adjusting for gestational age at delivery (See appendix for standardized respiratory questionnaire administered). Neurodevelopmental scores will be analyzed with the same general approaches described for the primary outcome of V_A in Specific Aim 1.

Intention to treat analysis will be used for the primary analysis of all aims. In addition, all of the aims will also be analyzed with the same general approach using a per protocol analysis and "as treated analysis".

Sample Size and Power Considerations. No studies have compared V_A at 6 months of age in stable infants randomized to eCPAP versus CPAP discontinuation in the NICU. Data from our pilot eCPAP study showed a 12% higher FRC in infants randomized to eCPAP at the end of two week treatment period¹. A study by [name] et al reported a 16% difference in both V_A and D_L in preterm infants according to CPAP treatment in the NICU (Table 1)² and a 12% difference in D_L between infants with BPD versus healthy term infants³. Therefore,

we powered our randomized trial to detect a 12% difference in V_A between the eCPAP and CPAP discontinuation groups.

Using ANCOVA model and assuming a mean V_A of 642 mL (SD=189) based on data of the overall mean and SD from the

Table 1. Estimated power for 34 infants per group with completed PFT data

Macan (SD) in _____ Estimated Power for Group Differences

Outcome Measures	Mean (SD) in Control Group	Estimated Power for Group Differences		
		12%	15%	17%
Alveolar volume (V _A)	642 (189)	80	92	97
Lung diffusing capacity (D _L)	4.1 (1.19)	80	92	98
Forced Expiratory Flow (FEF ₅₀)	346 (129)	35	49	60

control and CPAP groups reported in Assaf et al², a sample size of 34 infants per group is needed to yield 80% power for detecting a 12% difference (effect size=0.42) in V_A in the eCPAP group at α =0.05. This sample size also allows us to detect a 12% difference in D_L with an effect size of 0.42. We estimate that 18% of the study patients will be twin pairs based on our pilot eCPAP study. Conservatively counting just one infant out of each twin pair for sample size estimation, we will need 38 infants per group (76 total infants at 6 months) with completed V_A outcomes. We further assume a 10% missing data in the NICU (unsuccessful test or infants transferred to another facility) and a 15% loss from NICU discharge to the 6 month PFT (cohort loss, unacceptable PFT, unsuccessful sedation) and therefore we will need to randomize and/or assign 50 infants per group (total n=100) into the trial. This sample size will provide 80% power for detecting an effect size difference of 0.42 in outcome measures between the two groups in Aim 1 (primary outcome of V_A) and Aim 2 for D_L . This sample size allows us to detect a 23% difference in FEF₅₀.

With regards to the exploratory clinical respiratory outcome, published data in 48 preterm infants with average GA of 28 weeks who did not develop BPD (similar to the group we project to recruit) reported a 48% incidence of wheeze in the first year of life 4 . These researchers also documented a 21% incidence of wheeze in 195 term infants. In our initial vitamin C study 5 using the same questionnaire we will use in this proposed eCPAP study, 76 term infants born to non-smokers had a 27% incidence of wheeze in the first year of life. Based on these data, we project that 48% of the infants who have CPAP discontinued by the CPAP stability criteria will have wheeze in the first year of life. With our projected sample size of 50 per group accounting for a 15% missing questionnaire rate, we will have 70% power to show a decrease in the incidence of wheeze from 48% to 21%, and 90% power to show a decrease in wheeze and cough from 79% to 50%.

Interim analysis and stopping rules. No interim analysis for efficacy is planned. There will be no prespecified stopping rules, but the DSMB will review SAEs as they occur. Although this is a fragile population, based on our pilot eCPAP study, the fact that infants will be convalescing by the time they are enrolled in the study, and our experience with sedation in the VCSIP, we do not anticipate a large number of SAEs but will be vigilantly monitoring. The DSMB chair may call a DSMB meeting to specifically review safety concerns.

References:

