Forced Expiratory Flows (**FEF**₅₀) (**Secondary Outcome**) Measurements in triplicate will be obtained using the raised volume thoracic compression technique that we developed, and previously described^{74,75;83}.

Chloral hydrate sedation: Infant PFTs will be performed at Doernbecher Children's Hospital in sleeping infants following chloral hydrate sedation, as previously described^{68;74;84}. For testing, infants are examined by a physician and continuously monitored by a sedation nurse or health care provider certified in sedation and a respiratory therapist. The parents will be counseled about possible side effects, sign a separate sedation consent, and be given the patient education-discharge instructions. Safety will be monitored as outlined in the DSMB charter.

e. Respiratory Questionnaires

After discharge, a validated respiratory questionnaire will be administered monthly to the infant's primary caregiver ^{83;96} by research personnel blinded to the treatment allocation of eCPAP versus dCPAP in the NICU.. Caregivers are asked about new episodes of wheezing in the previous month, as well as administration of prescribed medications, other illnesses, trips to the emergency room, and hospitalizations. If an infant has wheezing associated with an illness lasting up to seven days, this will be counted as one episode. These questionnaires will be administered in person at the PFT done at approximately 6 months of CGA while the

remainder of the monthly questionnaires will be administered by phone. A small time reimbursement will be available for those patients after each questionnaire is completed.

f. Neurodevelopmental Testing

All preterm infants born at <34 GA are examined in the OHSU Developmental Evaluation Clinic (DEC) if born at OHSU or the PHSW DEC clinic if born at PHSW.at 6 -12 months CGA. This assessment is the standard practice of their care. We will document the Bayley IV neurodevelopmental scores for cognitive, receptive language, expressive language, fine motor, gross motor, and audiology results from these visits^{97;98}. The personnel performing this testing will be blinded to the treatment allocation of eCPAP versus dCPAP in the NICU.

g. Cohort Retention Methods

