Appendix: Clinical Respiratory Outcome

The wheeze outcome quantified between the infant's discharge from the Neonatal Intensive Care Unit through 12 months of age was obtained from the following specific questions contained on the standardized respiratory questionnaire^{1,2} which was administered monthly to the child's primary caretaker. A positive response to any of these questions on one or more respiratory questionnaire was recorded as a positive for the wheeze outcome. (The numbers below refer to the question number on the respiratory questionnaire and are organized by source: parental report; healthcare provider; medication use)

Field Label	Response Required/ Composite Notes (which to count)
PARENTAL REPORT	
Since [birth/the last time we talked] has your child had wheezing or whistling in his/her chest?	Any yes, ever. Include an overall count of individuals that answered yes as well as a second count of individuals that reported yes 2 or more times
14. Has child had any of the following illnesses?	14c. Bronchitis=1 (Yes)
	14d. Bronchiolitis=1 (Yes)
HEALTHCARE PROVIDER	
2. Since [birth/the last time we talked] has a health care provider said that your child has wheezy or asthmatic bronchitis?	Response = 1 (Yes)
3. Since [birth/the last time we talked] has a health care provider said that your child has asthma?	Response = 1 (Yes)
18. Reason for hospitalization code	Response = 3 (Bronchitis) or 4 (Bronchiolitis) or 5 (Wheezing) or 8 (Asthma/asthma exacerbation)
19. Not counting hospitalizations, has [CHILD] been seen by a doctor or health care provider because of problems with wheezing, asthma, or wheezy or asthmatic bronchitis, since [birth/the last time we talked]? Include visits to an emergency room, a doctor's office, urgent care, or clinic.	Response = 1 (Yes)
MEDICATION USE	
4a. Since the last time we talked, OR in the last 12 months, which of the following types of medication has child been given?	4a1. Bronchodilator inhalers/nebulizers, pills, or syrups= 1 (Yes)
	4a2. Steroid inhalers/nebulizers= 1 (Yes)
	4a3. Leukotriene modifiers=1 (Yes)
	4a4. Steroid pills or liquids= 1 (Yes)
	4a6a. If other, specify medication types. Refer to wheeze_med1=1 (Checked)
10b. Has child been given any medicine for a cough when he/she did not have a cold?	10b1a. Bronchodilator inhalers/nebulizers, pills, or syrups= 1 (Yes)
	10b1b. Steroid inhalers/nebulizers= 1 (Yes)

Field Label	Response Required/ Composite Notes (which to count)

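### Infants last contacted between 4 and 12 months with no wheeze so far are analysed as wheeze-free for the whole window, because the ever/never logistic model ignores time followed

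*SAP*

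**What the plan says.** Four statements in the SAP combine here.

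- **Who has the outcome** (Population, Clinical Respiratory Outcome Done): "Have at least one respiratory questionnaire completed at 4 months of corrected age or". The text breaks off there. That is an extraction gap, not a fault in the plan.
- **How wheeze is scored** (Appendix, Clinical Respiratory Outcome): "A positive response to any of these questions on one or more respiratory questionnaire was recorded as a positive for the wheeze outcome". There is no matching rule for scoring an infant negative.
- **How it is compared** (Specific Aim 3): "Logistic regression models will be used to compare the incidence of wheeze and the incidence of wheeze and cough between the two groups", adjusted for gestational age at delivery. No offset, censoring, weighting or follow-up time is mentioned.
- **What the power statement allows** (Sample Size and Power Considerations): 50 per group, "accounting for a 15% missing questionnaire rate", giving 70% power for a fall in wheeze from 48% to 21%.

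The window is described in two ways. The appendix runs from NICU discharge "through 12 months of age was obtained from the following specific questions contained on the standardized respiratory questionnaire". Aim 3 covers respiratory morbidity and "neurodevelopmental outcomes through 12 months of corrected age".

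On data collection, the protocol (Respiratory Questionnaires) says that "a validated respiratory questionnaire will be administered monthly". The main item looks back to the previous contact: "Since [birth/the last time we talked] has your child had wheezing or whistling in his/her chest".

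**The concern.** Take an infant whose last questionnaire is shortly after 4 months corrected age, with only negative answers. It meets the rule for having the outcome and has no positive item. In a binary model it can enter only as a non-event, exactly like an infant followed to 12 months without wheeze. The months after last contact are treated as observed and wheeze-free.

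Two things follow. Incidence is understated in both arms, which matters because Aim 3 is meant to supply pilot data for a multi-center trial. And if more infants are cut short in one arm, a difference appears that is not a treatment effect. Parents can know the allocation, since the protocol does not blind the NICU phase, so unequal loss is possible.

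The protocol's Missing Data section does not clearly catch this. It compares infants with outcome measures against those lost, and adds sensitivity analyses if missing at random fails. A partly followed infant already has the outcome, so it need not enter either step.

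**Working it through.** **1. The plan's own figure.** n = 50 × 0.85 = 42.5 per group, two-sided α = 0.05 (sidedness is not stated; assumed). Fisher's exact test by full enumeration gives 68.4% power at n = 42 and 69.9% at n = 43, so the stated 70% reproduces. That calculation treats 15% as wholly missing and everyone else as fully observed.

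The comparisons below use the simpler pooled test:

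power = Φ{[d − 1.96·√(2p̄(1−p̄)/n)] / √[(p₁(1−p₁)+p₂(1−p₂))/n]}

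With p₁ = 0.48, p₂ = 0.21, p̄ = 0.345 and n = 42.5 this is Φ[(0.27 − 1.96 × 0.1031)/0.0989] = Φ(0.69) = 75%. Read later values against 75%, not against the SAP's 70%.

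**2. Share of the window seen by 4 months corrected age.** Inputs from the protocol's pilot data: mean birth gestation 28.7 and 29.5 weeks by arm (midpoint 29.1) and discharge near 36 weeks. Term is taken as 40 weeks, and 4 months as 4 × 52/12 = 17.3 weeks.

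- Covered: 40 + 17.3 − 36 = 21.3 weeks.
- Window to 12 months corrected age: 40 + 52 − 36 = 56 weeks; 21.3/56 = 38%.
- Window to 12 months of age: 29.1 + 52 − 36 = 45.1 weeks; 21.3/45.1 = 47%.

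**3. Recorded risk in a truncated infant.** Assumption, not in the documents: constant hazard of first wheeze. With share f of the window observed, recorded risk = 1 − (1 − p)^f.

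| True risk | f = 0.38 | f = 0.47 |
|---|---|---|
| 48% | 1 − 0.52^0.38 = 22% | 1 − 0.52^0.47 = 26% |
| 21% | 1 − 0.79^0.38 = 9% | 1 − 0.79^0.47 = 10% |

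**4. Equal truncation in both arms.** Recorded rate = (1 − q)p + q[1 − (1 − p)^f], where q is the share truncated among the 42.5 per group. The value 6% is 100% minus the 94% questionnaire completion that the protocol (Cohort Retention Methods) reports for the group's earlier vitamin C trial. The value 15% borrows the SAP's missing rate as an illustration.

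| q | Recorded rates (f = 0.38 / 0.47) | Difference, points | Pooled power |
|---|---|---|---|
| 0 | 48% vs 21% | 27 | 75% |
| 6% | 46.4 vs 20.3 / 46.7 vs 20.4 | 26.2 / 26.3 | 73% / 74% |
| 15% | 44.1 vs 19.1 / 44.8 vs 19.4 | 25.0 / 25.4 | 70% / 71% |

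**5. No true effect (48% in both arms), unequal truncation.** The imbalances are assumptions; the documents give none.

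| Truncated, eCPAP vs dCPAP | f = 0.38 | f = 0.47 |
|---|---|---|
| 9% vs 3% | 45.7 vs 47.2: −1.6 points, OR 0.94 | 46.1 vs 47.4: −1.3 points, OR 0.95 |
| 25% vs 5% | 41.5 vs 46.7: −5.2 points, OR 0.81 | 42.6 vs 46.9: −4.3 points, OR 0.84 |

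With the imbalance reversed, the sign reverses and a real benefit would be partly hidden.

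**The case against.** Much of the case on the other side stands.

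- **The 4-month condition.** A reader might infer that any infant lost early is scored wheeze-free. The documents do not support that. If the lost words mean 4 months or later, infants lost before 4 months corrected age do not have the outcome and are left out. Any further condition in the lost text is unseen and cannot be held against the plan.
- **One questionnaire is not in itself the defect.** Items ask about the time since birth or the last contact, so a single late questionnaire covers earlier gaps. Only an early last contact matters. Infants who wheezed before loss are scored correctly.
- **The 6-month visit.** The protocol gives one questionnaire in person at the lung function visit. Infants attending at 6 months corrected age are seen for (40 + 26 − 36)/56 = 54% or 30/45.1 = 67% of the window, which would record a 48% risk as 30–35% rather than 22–26%. The SAP does, however, accept alveolar volume tests from 4 months corrected age.
- **Likely scale.** The one completion figure from a finished study that used monthly questionnaires through 12 months is 94%, which points to the small end of the tables. It comes from offspring of pregnant smokers, so it is a guide and not a guarantee for this cohort. No document supports a large imbalance between arms; parents knowing the allocation makes one possible, no more.
- **Missing-data plans.** The protocol expects loss for the respiratory outcomes and plans sensitivity analyses. These do not explicitly address partial follow-up, and the SAP has no missing-data section.

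What remains is the gap between the 4-month qualifying point and the 12-month endpoint, which neither document addresses.

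**Conclusion.** The point holds as a minor one. Infants who qualify at about 4 months corrected age, have no wheeze so far and are lost before 12 months enter the logistic model as wheeze-free for the full window. The negative coding is an inference from the ever/never rule, though the SAP offers no alternative.

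At 6% truncated the effect is slight. At 15% truncated the contrast loses about 2 points and pooled power about 4 to 5 points. With no true effect, a spurious difference needs unequal truncation, and exceeds about 2 points only at imbalances that the documents give no reason to expect. All sizes rest on constant hazard, last contact exactly at 4 months corrected age, and the pilot's birth and discharge ages.

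Wheeze is exploratory, so the primary and secondary conclusions are untouched. The reason to act is that these incidence figures are intended for planning a later trial.

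**What to change.** In SAP Specific Aim 3, add an analysis that uses time observed: a discrete-time complementary log-log model for first wheeze on the monthly questionnaires, censored at the last completed one, adjusted for gestational-age stratum and clustered by family. Report it beside the ever/never logistic model, and tabulate age at last questionnaire by arm. State how an infant with only negative answers and incomplete follow-up is coded. Settle whether the window ends at 12 months of age or of corrected age.

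A simpler option is an ever/never complementary log-log model with log(months covered) as offset. It is valid only under constant hazard, so it is not equivalent to the discrete-time model.

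The cost is SAP wording and light programming on data already collected. The added effect measure is a hazard ratio. Month of onset is only approximate across missed contacts. Censoring is assumed non-informative given the covariates, so the model does not remove bias where loss is itself related to wheeze risk.

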Preterm delivery is the most common cause of altered lung development with potential lifelong sequelae. and prematurity is a global health crisis^{23;24}. The origins of adult respiratory disease can be traced back to the fetal/early childhood period when the lung undergoes rapid development. Our laboratory has shown that infants born at 30-35 weeks GA with no clinical respiratory disease after birth had decreased airway function with lower forced expiratory flows (FEFs) in the first year of life, which lasted into the second year of life⁴. This confirms findings of other birth cohorts that individuals track along the lung function percentile that is established early in life²⁵. This emphasizes the need to optimize lung function/growth in fetal and early postnatal life. Multiple risk factors for prematurity have been identified, but little progress has been made to find interventions to stimulate lung growth¹. We, and others^{14-16;26-28} have strong pilot animal and human data that mechanical strain of the lung from continuous positive airway pressure (CPAP) may be a simple, safe, and non-pharmacologic stimulus to promote lung growth, improve lung function, and decrease airway reactivity. Although CPAP is the standard of care for preterm infants with respiratory distress, there is little evidence defining the optimal time to discontinue CPAP in stable preterm infants¹⁰. We have promising data randomizing stable preterm infants (≤ 32 weeks GA treated with CPAP for respiratory distress) to extended CPAP [(eCPAP) extra 2 weeks] versus CPAP discontinuation. The eCPAP resulted in increased lung volumes at the end of treatment and at discharge¹⁶. This study did not perform pulmonary function tests (PFTs) after discharge. Our goals in this proposal are to test the hypothesis that eCPAP in stable premature infants will stimulate lung growth and improve lung function as measured at 6 months of age.

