Infant pulmonary function testing will be performed when CPAP stability criteria is met prior to randomization and at the end of the two week treatment period. Studies will be performed with the infant supine, quietly asleep and at least 30 minutes after a feed. All measurements will be obtained using a computerized infant pulmonary function cart (SensorMedics 2600; SensorMedics Inc, Yorba Linda, CA; Jaeger/Viasys Master Screen Baby Body) in the OHSU NICU at the infant's bedside. Standard testing criteria outlined by the American Thoracic Society / European Respiratory Society will be met ^{81;93,94}. Tidal breathing will be recorded with up to 50 flow-volume loops⁴⁶. Passive respiratory mechanics (respiratory compliance [Crs] and respiratory resistance [Rrs]) will be obtained using the single breath occlusion technique⁹⁵. Functional residual capacity (FRC) will be obtained with the nitrogen washout technique with acceptance criteria as per ATS/ERS guidelines⁹⁴. Vital signs (respiratory rate, heart rate, oxygen saturation) will be continuously monitored during the testing. If a PFT does not meet the pre-specified technically acceptable criteria it can be reattempted in 24-48 hours.

d. Outpatient Infant Pulmonary Function Tests

Infant pulmonary function testing will be performed at 6 months of CGA (range of 5-8 months corrected age) at OHSU for all randomized patients. These will be primarily directed and performed by [name] who will be blinded to the NICU treatment allocation. [name] has experience with measurements of V_A, D_L,

and FEFs as these are the PFTs that were performed in the study at the Oregon National Primate Research Center examining the effect of CPAP on lung development. [name] RRT will also be a part of the research team performing the 6 month PFTs and he will be blinded as well. He was an integral part of the successful VCSIP study^{83,84} which measured FEFs at 3 and 12 months of age in offspring of pregnant smokers randomized to vitamin C versus placebo during pregnancy. Standard acceptance criteria will be applied. The PFT results will be reviewed off site for acceptability, reproducibility, and completeness by [name] and/or [name], RRT who has over ten years of experience in [name] PFT laboratory performing and interpreting these tests. They will be blinded to the treatment allocation in the NICU as will the statisticians at Indiana University performing the data analysis.

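### Pre-randomization FRC is not a prespecified covariate in the primary V_A model and can enter only through a significance test for baseline imbalance, which may give up some precision

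*SAP*

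**What the plan says.** **Model.** SAP, Specific Aim 1, compares V_A between arms while "adjusting for gestational age at delivery (randomization stratification variable) and other baseline variables that are found to be statistically different between the two groups". It then says "we will further adjust for length and sex in the GLMMs as indicated". Protocol 7.b1 describes the same model and adjusts for length and sex without that last qualifier. Neither text names FRC as a covariate.

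**Baseline measurement.** Protocol 6.c: "Infant pulmonary function testing will be performed when CPAP stability criteria is met prior to randomization", and again after the two treatment weeks. In the same section, "Functional residual capacity (FRC) will be obtained with the nitrogen washout technique". Compliance, resistance and tidal loops are recorded too, but FRC is the only static lung volume listed.

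**Role given to it.** SAP, Specific Aim 2, lists "FRC measurements in the NICU done pre and post randomization" among the measurements to be analyzed, not among the adjusters for V_A.

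**Background.** Protocol 2.a says that "individuals track along the lung function percentile that is established early in life".

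**Sample size.** The SAP and Protocol 7.a cite an ANCOVA with mean V_A 642 mL, SD 189 mL, a 12% difference and 34 infants per group for 80% power "in the eCPAP group at α =0.05". They name no covariates and no explained variance for that ANCOVA.

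**The concern.** A baseline covariate earns its place in a randomized analysis by predicting the outcome. The plan instead admits covariates beyond gestational age, length and sex by testing whether the arms differ. Under proper randomization such a test, at an assumed 5% level, flags any given variable about once in twenty trials. FRC would therefore be left out about 95% of the time, however prognostic it is.

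The sponsor itself treats NICU FRC as relevant to V_A: the pilot's 12% FRC difference is one of the grounds for the 12% V_A target. What is at stake is precision, together with a covariate set that would be settled by the trial data. The plan also has no rule for infants without a baseline FRC if the test does bring it in. Protocol 7.c deals with loss to follow-up on outcomes, and the SAP has no missing-data section.

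**Working it through.** **1. The plan's own figure.** Inputs from the SAP, Sample Size and Power Considerations: mean 642 mL, SD 189 mL, difference 12%, α = 0.05, 34 per group. Sidedness is not stated, so two-sided is assumed.

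- Difference = 0.12 × 642 = 77.0 mL; d = 77.0/189 = 0.408 (the SAP states 0.42).
- Without covariates, n = 2(1.960 + 0.842)²/d² gives 95 per group at d = 0.408 and 89 at d = 0.42. Power at 34 per group is about 38–41%, not 80%.
- With 34 per group, 80% power needs d = 0.690 (noncentral t, 66 df). Covariates must therefore explain R² = 1 − (0.408/0.690)² = 0.65, or 1 − (0.42/0.690)² = 0.63. The normal approximation gives 0.64 and 0.62. One-sided, the requirement at d = 0.408 is about 0.54–0.55.
- The later steps do reproduce: 34/0.91 = 37.4, so 38; 38/(0.90 × 0.85) = 49.7, so 50.

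The stated power thus already relies on an unstated R² of about 62–65%.

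**2. What FRC could add.** Let r be the partial correlation of baseline FRC with 6-month V_A given gestational age, length and sex. **The documents give no r; the values below are assumptions.** Residual variance is multiplied by (1 − r²), so power is evaluated at d = 0.690/√(1 − r²). If a share m of baseline FRC is missing and imputed, r² is replaced approximately by r²(1 − m). Here m = 0.10, borrowed from the SAP's NICU missing-data allowance.

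| Assumed r | Variance removed | Power, FRC complete | Power, 10% imputed | n per group for the same power (34 × (1 − r²)) |
|---|---|---|---|---|
| 0.1 | 1% | 80.4% | 80.4% | 33.7 |
| 0.2 | 4% | 81.6% | 81.4% | 32.6 |
| 0.3 | 9% | 83.6% | 83.2% | 30.9 |
| 0.4 | 16% | 86.4% | 85.7% | 28.6 |

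The confidence interval narrows by 1 − √(1 − r²), which is 0.5%, 2.0%, 4.6% and 8.3%. Starting instead from the unadjusted inputs (39.0% power by the normal approximation, d = 0.408), the same r values give 39.3%, 40.3%, 42.1% and 45.0%.

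**3. If infants without FRC were dropped.** Variance changes by (1 − r²)/(1 − m). With m = 0.10 this is +6.7% at r = 0.2, +1.1% at r = 0.3 and −6.7% at r = 0.4. Break-even is r = √m = √0.10 = 0.32. Below that, adjustment on complete cases loses precision.

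**4. How coarse the imbalance screen is.** The pilot FRC SDs at randomization (Protocol Table 2) are 11.8 and 10.6 mL, pooled √((11.8² + 10.6²)/2) = 11.2 mL. The smallest significant difference is t × √(2/n) SDs.

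- 50 per arm: 1.984 × √(2/50) = 0.40 SD, or 4.5 mL.
- 34 per arm: 1.997 × √(2/34) = 0.48 SD, or 5.4 mL.

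As an illustration, take r = 0.3 and a residual V_A SD of 189 × √(1 − 0.65) = 112 mL. An unflagged 0.40 SD imbalance in the part of FRC that the other covariates do not explain would then shift that trial's estimate by 0.3 × 0.40 × 112 = 13 mL, against a 77 mL target. This is a chance shift in one realization and averages to zero over randomizations.

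**The case against.** The strongest reply is that this is a choice among defensible covariate sets. The documents name length and sex as the main determinants of lung function, and both are planned. They may already carry most of what FRC would contribute. FRC by nitrogen washout in the NICU and V_A at 30 cmH2O under sedation months later are different measurements. At r = 0.1 the gain is 0.4 power points, and at r = 0.3 or below it is under 4. All of that stands, and it limits the size of the point.

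Four stronger readings are tempting, and the documents do not support them:

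- **That FRC is excluded.** It is conditional: a significant imbalance would bring it in, so the larger chance imbalances are covered.
- **That it is the best available baseline predictor, as the protocol's tracking statement shows.** No correlation is given, and the pilot measured no lung function after discharge. The tracking sentence is background that follows airway-flow data from the first and second years of life. It does not link NICU FRC to later V_A.
- **That the gain is free.** Neither list of randomization criteria requires an acceptable FRC, and a failed test can be, but need not be, reattempted. Protocol 6.c places the inpatient equipment in the OHSU NICU while PHSW also recruits, so missingness could exceed 10%. The gain depends on a rule for missing values.
- **That the primary comparison is biased without FRC.** It is not; randomization protects it.

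What remains is that the entry rule uses the wrong criterion, and that the plan does not say what happens to infants without FRC if the rule fires.

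**Conclusion.** The point holds as one of precision and prespecification. Pre-randomization FRC should not depend on a significance test to enter the V_A model, particularly when the stated power already needs covariates to explain about 62–65% of the variance.

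The benefit is uncertain: about 0.4 to 6.4 power points for an assumed partial r of 0.1 to 0.4, on a nominal 80%, and nothing if r is near zero. These figures assume a two-sided test, 34 effective infants per group and the plan's 80% taken at face value. The unexplained R² behind that 80% is a separate and larger matter, which adding FRC does not resolve. The change is worth making because it is cheap and replaces a data-driven choice in the primary analysis, not because a large gain has been shown.

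**What to change.** Before treatment codes are released to the analysts, add one sentence to SAP, Specific Aim 1: pre-randomization FRC is a fixed covariate in the V_A model regardless of any baseline comparison, and infants without an acceptable baseline FRC are kept by mean imputation (mean over both arms) plus a missing indicator. If V_A is transformed to logs, enter FRC on the log scale.

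**Cost:** one or two degrees of freedom and no new measurements. The restriction to observe is that no randomized infant with a V_A outcome leaves the ITT analysis for want of FRC; with 10% missing, dropping them would lose precision below r of about 0.32.

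Carrying FRC into the DLCO and FEF models, which follow the V_A approach, is optional. No figure in the documents supports a gain there.
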